## **Abstract**

- **Background:** This web-based experimental study aims to investigate the effect of promoting an active (i.e. conscious and autonomous) choice process regarding coping with an increased risk of

cardiovascular disease (CVD) on psychological outcomes, compared to usual care; i.e. a general practitioners' (GP) advice. Coping strategies include: changing one's lifestyle; taking medication; doing both; or changing nothing. An active choice process is expected to increase psychological outcomes compared to a passive choice process (i.e. a simple advice).

- **Methods:** We will recruit adults aged 45-65 years who are not on medication to prevent CVD and who do not have are have had CVD. Participants will be randomized to the intervention – active choice – group or the control – usual care – group. Both groups will be presented a hypothetical CVD risk. In the control group, the risk will be presented as a 31% risk of developing CVD within ten years, whereas the intervention group will be presented an equivalent risk in a different format: a 'heart age' of 16 years older than their actual age. The intervention group will additionally receive information about the meaning of the risk, including its causes and potential consequences, and about the four coping strategies. The pros and cons of each strategy will be presented, followed by a value-clarification exercise. The control group will read a hypothetical advice to change their lifestyle, and to take medication to lower their CVD risk. Participants will receive a questionnaire that assesses psychological outcomes, including 'degree of active choice', commitment, and intention to cope with CVD risk. Intergroup differences will be examined by regression analyses. In addition, we will conduct a process evaluation.
- **Discussion:** If an active choice process regarding coping with an increased CVD risk indeed results in better outcomes compared to an advice, the active choice intervention could be implemented by GP's. GP's could either use it as a tool during their consultation, or send it to their patients, so the patients can read the information and clarify their own values before making a choice. Providing patients with a choice – instead of giving advice – respects their autonomy. Ultimately, it is expected that an active choice process will increase patients' adherence to the chosen option; e.g., a healthier lifestyle or medication use.
- **Trial registration:** Prospectively registered at [clinicaltrials.gov](http://clinicaltrials.gov); 19-11-2021.

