## Introduction

### Background and rationale {6a}

Cardiovascular disease (CVD) continues to be a leading cause of mortality among adults. Adults at increased risk of cardiovascular disease are usually advised by their general practitioner (GP) to change their lifestyle (i.e., quit smoking; eat healthier; become more physically active). In addition, GP's regularly

advise their patients to take antihypertensive and/or lipid lowering medication to decrease the CVD risk. Previous research has shown that many patients at increased risk of CVD have difficulty maintaining lifestyle changes and adhering to their medication regimen – either intentionally or unintentionally. Intentional non-adherence could occur when patients experience side-effects of the medication, whereas unintentional non-adherence usually occurs when patients forget to take their medication.

In the current study, we will investigate whether promoting an active choice regarding coping with an increased CVD risk results in better psychological outcomes (e.g., degree of active choice; commitment toward the chosen option) compared to usual care (i.e. a GP's advice to change one's lifestyle and take medication). By 'active choice' we mean a conscious and autonomous choice in which an individual (a) becomes aware of a discrepancy between the current and desired situation; (b) understands what his/her CVD risk means, and what its causes and consequences are; (c) evaluates the pros and cons of the different options to cope with the risk; and (d) is clear about his/her values regarding the choice. The different options to cope with an increased CVD risk include: changing one's lifestyle; taking medication; doing both; or changing nothing.

We will investigate this in a web-based RCT among adults aged 45-65 years. The intervention group (i.e. active choice group) and control group (i.e. usual care group) will both receive a hypothetical CVD risk. We expect an active choice regarding coping with an increased CVD risk to result in better psychological outcomes compared to a GP's advice. Ultimately, a more active choice is expected to result in greater behavioural persistence regarding the chosen option; i.e. lifestyle change and/or medication adherence.

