## **Objectives {7}**

To test the effect of an online active choice intervention regarding coping with increased risk of cardiovascular disease on psychological outcomes among adults aged 40 to 65 years, and to investigate whether effects differ between men and women.

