## **Interventions**

### **Explanation for the choice of comparators {6b}**

The control group will receive online information and advice that resembles GP's usual care. This is expected to promote a relatively passive choice process regarding 'how to cope with an increased risk of CVD', since participants receive an advice and are not asked to actively think about their values and preferences.

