### **Intervention description {11a}**

The intervention group will be presented a hypothetical 'heart age' of 16 years older than their actual age. They are asked to imagine that this heart age really applies to them. Next, participants will receive information about the meaning of the risk, including its causes and potential consequences, and about four coping strategies: changing one's lifestyle; taking medication; doing both; or changing nothing. The pros and cons of each strategy will be presented, followed by a value-clarification exercise.

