## Outcomes {12}

All outcomes will be assessed directly after the intervention. Overview of outcome measures:

Outcome	Number of items	Scale
Intention regarding coping with CVD	1	Nominal; 4 options: Lifestyle change/ Medication use/ Lifestyle change and medication use/ Change nothing
Intention strength	1	Scale of 1 (not strong at all) to 10 (very strong)
Degree of active choice	11	A 5-point scale will be used for the items (1: totally disagree; to 5: totally agree). The average of all 11 items will be used as composite score.
Values congruence	1	A 10-point scale will be used: 1 (not at all) to 10 (totally).
Commitment	3	A 10-point scale will be used: 1 (not at all) to 10 (totally).
Self-efficacy	1	A 10-point scale will be used: 1 (not at all) to 10 (totally).
Response efficacy	2	A 10-point scale will be used: 1 (not at all) to 10 (totally).
Autonomous motivation & controlled motivation	12	The Treatment Motivation Questionnaire will be used. This questionnaire contains 2 subscales: Autonomous motivation and Controlled motivation. Items are on a scale of 1 (not at all true) to 7 (very true).
Knowledge – illness representations	4	4 items on a scale of 1 (totally disagree) to 5 (totally agree).
Risk perception: Cognitive and affective risk appraisal	3	1 item assesses cognitive risk appraisal (on a scale ranging from 'very small risk' to 'very high risk'. 2 items assess affective risk appraisal on a scale of 1 (not at all) to 10 (totally)
Lifestyle intention	1	Nominal; 4 options: Quit smoking; Healthier diet; More physical activity; Other.
Lifestyle intention strength	1	Scale of 1 (not strong at all) to 10 (very strong)
Perceived health	1	Item from RAND-36. Scale: 1 (very bad) to 5 (very good).
Preferred decision-making role	1	Item based the Control Preferences Scale of Degner et al. (1992). Contains 5 options to assess preference for a more passive or more active role in decision-making about treatment.

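### Does calling a fixed 31% ten-year risk and a heart age of actual age plus 16 equivalent undermine the comparison of the two arms?

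*Protocol*

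**What the plan says.** Under Methods in the Protocol's Abstract, the control arm is described as follows: "the risk will be presented as a 31% risk of developing CVD within ten years". The other arm's risk statement is said to match it: "whereas the intervention group will be presented an equivalent risk in a different format". That format puts the participant's heart 16 years ahead of his or her own age. Intervention description {11a} repeats the heart age and adds: "They are asked to imagine that this heart age really applies to them". Neither place gives a risk model, a reference age or sex, or any tailoring of the 31%. Eligibility criteria {10} admit ages 45 to 65.

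The arms differ in more than risk format. The intervention arm also gets an explanation of the risk, four options with their advantages and drawbacks, and a values exercise. For the comparator, Protocol {6b} says: "The control group will receive online information and advice that resembles" what a GP usually provides.

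The target of inference is worded in two ways. The Abstract's Background speaks of the process: "An active choice process is expected to increase psychological outcomes compared to a passive choice process (i.e. a simple advice". Objectives {7} speaks of the package: "To test the effect of an online active choice intervention regarding coping with increased risk of cardiovascular disease on psychological outcomes". The SAP's Research question and Hypothesis ask about promoting one process or the other, and its Design section sets one whole condition against the other. Every SAP model has condition as the independent variable, with age added only if it is found to confound.

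**The concern.** Two things look wrong.

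First, one arm sees a constant and the other sees a figure that moves with age. A constant and a strictly rising quantity cannot agree over a 20-year age range. If the arms were shown different levels of risk, and not just different formats, part of any difference between them could come from the risk statement.

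Second, two arms give one contrast. If the report credits active choosing, the contribution of the heart-age format cannot be separated out. Cognitive and affective risk appraisal are most exposed, because those items (Outcomes {12}: "1 item assesses cognitive risk appraisal", with two more for affect) ask about the very risk that was stated differently. At stake is whether a difference could be attributed to the choice process or only to the intervention as delivered.

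**Working it through.** **1. The plan's own figure.** The equivalence cannot be reproduced, because the documents give no definition of heart age and no risk function.

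**2. What participants see.** Inputs: ages 45 to 65 (Protocol {10}); heart age = age + 16 (Abstract, {11a}); 31% in control (Abstract).
- Heart age at 45: 45 + 16 = 61. At 55: 71. At 65: 81.
- Span: 81 − 61 = 20 years, over 65 − 45 + 1 = 21 whole-year ages.
- Objectives {7} words the range as 40 to 65. That would give heart ages 56 to 81 over 26 whole-year ages.

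**3. Exact matching.** Assume that, within each sex, risk r depends only on heart age and rises strictly. Then r(age + 16) = 31% has at most one solution per sex: at most 1 of 21 ages (4.8%). This is a test of exact equality, and any strictly varying quantity would fail it.

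**4. Approximate matching (illustration only).** The growth rate g per year of heart age and the anchor age of 55 are assumptions. With H = −ln(1 − 0.31) = 0.371,

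risk(a) = 1 − exp(−H × (1 + g)^(a − 55)).

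| g | risk at 45 | risk at 55 | risk at 65 |
|---|---|---|---|
| 1% | 28.5% | 31.0% | 33.6% |
| 2% | 26.2% | 31.0% | 36.4% |
| 5% | 20.4% | 31.0% | 45.4% |
| 8% | 15.8% | 31.0% | 55.1% |

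At g = 1%, 7 of 21 ages lie within one percentage point of 31%; at g = 5%, only 1 does. So the mismatch could be small or large, and the documents cannot say which. No described procedure shows these percentages to the intervention arm, and the risk is hypothetical in both arms.

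**5. What depends on the equivalence.** The sample size uses a 0.15-point difference in degree of active choice, alpha .05 and 80% power, with 206 men and 156 women per group: 2 × (206 + 156) = 724. Neither the 31% nor the 16 years enters it. The models regress each outcome on condition, so neither figure enters there either.

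**6. Which differences lie outside active choice.** Protocol {6a} defines active choice by four elements, (a) to (d).

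| Difference between arms | Place in the Protocol |
|---|---|
| Explanation of the risk | element (b): "understands what his/her CVD risk means, and what its causes and consequences are" |
| Options with advantages and drawbacks | element (c) |
| Values exercise | element (d) |
| GP-style advice in control | the comparator itself ({6b}) |
| Heart age instead of a percentage | not assigned; could serve (a) or (b), but no link is stated |

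Four of the five rows are the process being promoted or the comparator it is set against. Only risk format, with any mismatch in risk level, is left over.

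**The case for a change.** The best case for a change is that it would cost only words. *Equivalent* has no basis in the documents, and deleting it or giving its derivation would touch no arm, analysis or sample size. The Abstract and the Discussion use the language of process, which could carry into a publication. The process evaluation named in the Abstract has no described method for separating components. Age is not among the listed effect modifiers, so a mismatch that varies with age would go unexamined.

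Part of this stands. The word is unsupported as an exact claim, and a difference in risk appraisal cannot be assigned to the choice process alone.

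The rest is weaker. The Discussion's sentence is conditional and ends with implementing the intervention, not with a claim about mechanism. The SAP speaks of promoting a process and contrasts conditions. Randomisation balances age in expectation, so an age-dependent mismatch is part of what the intervention delivers and does not bias the package comparison. The proposed edits would remove a descriptive word from an abstract, restate Objectives {7} elsewhere and add a limitation that is already visible from the description of the arms.

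**Conclusion.** No change is needed, because none would improve the trial. Exact equivalence can hold at no more than 1 of 21 ages per sex, provided that risk depends only on heart age within each sex and rises strictly with it. The documents state neither condition, and they do not allow the real gap, or the size or direction of any effect on outcomes, to be calculated.

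The comparison of the whole intervention with usual care is valid whether or not the two risk statements match, and it is what Objectives {7} asks for. The outcomes most exposed, cognitive and affective risk appraisal, are not among the SAP's three primary outcomes (degree of active choice, intention strength and commitment). An analyst would read a difference in risk appraisal as the effect of the condition as delivered, including its way of stating the risk. That reading requires no amendment to the arms, the models or the sample size.

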## Keywords

*Cardiovascular disease, Decision making, Active choice, Patient autonomy, Prevention, Lifestyle change, Medication adherence; Randomized Controlled Trial*

## Introduction

### Background and rationale {6a}

Cardiovascular disease (CVD) continues to be a leading cause of mortality among adults. Adults at increased risk of cardiovascular disease are usually advised by their general practitioner (GP) to change their lifestyle (i.e., quit smoking; eat healthier; become more physically active). In addition, GP's regularly

advise their patients to take antihypertensive and/or lipid lowering medication to decrease the CVD risk. Previous research has shown that many patients at increased risk of CVD have difficulty maintaining lifestyle changes and adhering to their medication regimen – either intentionally or unintentionally. Intentional non-adherence could occur when patients experience side-effects of the medication, whereas unintentional non-adherence usually occurs when patients forget to take their medication.

In the current study, we will investigate whether promoting an active choice regarding coping with an increased CVD risk results in better psychological outcomes (e.g., degree of active choice; commitment toward the chosen option) compared to usual care (i.e. a GP's advice to change one's lifestyle and take medication). By 'active choice' we mean a conscious and autonomous choice in which an individual (a) becomes aware of a discrepancy between the current and desired situation; (b) understands what his/her CVD risk means, and what its causes and consequences are; (c) evaluates the pros and cons of the different options to cope with the risk; and (d) is clear about his/her values regarding the choice. The different options to cope with an increased CVD risk include: changing one's lifestyle; taking medication; doing both; or changing nothing.

We will investigate this in a web-based RCT among adults aged 45-65 years. The intervention group (i.e. active choice group) and control group (i.e. usual care group) will both receive a hypothetical CVD risk. We expect an active choice regarding coping with an increased CVD risk to result in better psychological outcomes compared to a GP's advice. Ultimately, a more active choice is expected to result in greater behavioural persistence regarding the chosen option; i.e. lifestyle change and/or medication adherence.

## **Objectives {7}**

To test the effect of an online active choice intervention regarding coping with increased risk of cardiovascular disease on psychological outcomes among adults aged 40 to 65 years, and to investigate whether effects differ between men and women.

## **Trial design {8}**

Parallel group design: intervention versus control (1:1)

## **Methods: Participants, interventions and outcomes**

### **Study setting {9}**

Web-based study conducted in the Netherlands among members of an online panel of a research agency.

### **Eligibility criteria {10}**

Inclusion criteria: Adults aged 45-65 years

Exclusion criteria: Suffering/ having suffered from CVD; being on lipid lowering or blood pressure lowering medication; Suffering from diabetes, kidney damage or rheumatism; not being able to walk at least 100

meters; being in a wheelchair; pregnancy.

### **Who will take informed consent? {26a}**

Participants eligible for inclusion will be informed about the study and data storage. Participants will subsequently be asked to provide (online) informed consent; if they provide consent (by clicking a button), they continue to the study.

### **Additional consent provisions for collection and use of participant data and biological specimens {26b}**

N/A

## **Interventions**

### **Explanation for the choice of comparators {6b}**

The control group will receive online information and advice that resembles GP's usual care. This is expected to promote a relatively passive choice process regarding 'how to cope with an increased risk of CVD', since participants receive an advice and are not asked to actively think about their values and preferences.

### **Intervention description {11a}**

The intervention group will be presented a hypothetical 'heart age' of 16 years older than their actual age. They are asked to imagine that this heart age really applies to them. Next, participants will receive information about the meaning of the risk, including its causes and potential consequences, and about four coping strategies: changing one's lifestyle; taking medication; doing both; or changing nothing. The pros and cons of each strategy will be presented, followed by a value-clarification exercise.

### **Criteria for discontinuing or modifying allocated interventions {11b}**

N/A

### **Strategies to improve adherence to interventions {11c}**

N/A

### **Relevant concomitant care permitted or prohibited during the trial {11d}**

N/A

### **Provisions for post-trial care {30}**

N/A

## Outcomes {12}

All outcomes will be assessed directly after the intervention. Overview of outcome measures:

Outcome	Number of items	Scale
Intention regarding coping with CVD	1	Nominal; 4 options: Lifestyle change/ Medication use/ Lifestyle change and medication use/ Change nothing
Intention strength	1	Scale of 1 (not strong at all) to 10 (very strong)
Degree of active choice	11	A 5-point scale will be used for the items (1: totally disagree; to 5: totally agree). The average of all 11 items will be used as composite score.
Values congruence	1	A 10-point scale will be used: 1 (not at all) to 10 (totally).
Commitment	3	A 10-point scale will be used: 1 (not at all) to 10 (totally).
Self-efficacy	1	A 10-point scale will be used: 1 (not at all) to 10 (totally).
Response efficacy	2	A 10-point scale will be used: 1 (not at all) to 10 (totally).
Autonomous motivation & controlled motivation	12	The Treatment Motivation Questionnaire will be used. This questionnaire contains 2 subscales: Autonomous motivation and Controlled motivation. Items are on a scale of 1 (not at all true) to 7 (very true).
Knowledge – illness representations	4	4 items on a scale of 1 (totally disagree) to 5 (totally agree).
Risk perception: Cognitive and affective risk appraisal	3	1 item assesses cognitive risk appraisal (on a scale ranging from 'very small risk' to 'very high risk'. 2 items assess affective risk appraisal on a scale of 1 (not at all) to 10 (totally)
Lifestyle intention	1	Nominal; 4 options: Quit smoking; Healthier diet; More physical activity; Other.
Lifestyle intention strength	1	Scale of 1 (not strong at all) to 10 (very strong)
Perceived health	1	Item from RAND-36. Scale: 1 (very bad) to 5 (very good).
Preferred decision-making role	1	Item based the Control Preferences Scale of Degner et al. (1992). Contains 5 options to assess preference for a more passive or more active role in decision-making about treatment.

## Participant timeline {13}

After clicking the link to the study and providing informed consent, participants will be randomized to the intervention or control group. Directly after the intervention, participants are asked to complete the questionnaire.

## Sample size {14}

The study is powered to detect 0.15 points difference in 'Degree of active choice' in men as well as in women, using an alpha level of .05 and a statistical power of 80%. This means that 206 men and 156 women are required per group. Since we have two groups, a sample size of n=724 is required (i.e., 412 men and 312 women).

## Recruitment {15}

The research agency will invite panel members by e-mail to participate. If needed, a few reminders will be

sent by e-mail to panel members to achieve adequate enrolment

## **Assignment of interventions: allocation**

### **Sequence generation {16a}**

Participants will randomly be assigned to the intervention or control group by the research agency.

### **Concealment mechanism {16b}**

Random allocation will be done by the computer.

### **Implementation {16c}**

The research agency will randomly assigned panel members to the intervention or control group.

## **Assignment of interventions: Blinding**

### **Who will be blinded {17a}**

Trial participants will be blind to the group they are assigned to; they will not be informed about the other groups.

### **Procedure for unblinding if needed {17b}**

N/A

## **Data collection and management**

### **Plans for assessment and collection of outcomes {18a}**

The questionnaire items are listed in the table of outcomes.

